### 10.9 Safety Follow-up

For the first 16 patients, patients will be treated in the study by sub-group (block) of 4. Before starting the treatment of a new block of 4 patients, a safety review at the end of the Visit #3 for the first block (48 hours of hospitalization and first follow-up visit at 2 weeks after implantation) and at the end of Visit #2 (48 hours hospitalisation or on-site visit) for the other blocks will be conducted. If from this review, 3 or more patients have not experienced SAE potentially related to the IMP, including severe AESC, and resulting in death, life-threatening, resulting in persistent or significant disability/incapacity, requiring intervention to prevent permanent impairment or damage, the next block of 4 patients will be allowed for treatment (Visit #2).

The members of the SMC will perform this safety monitoring analysis.

After inclusion of the first 16 assessable patients and based on 6-month treatment follow-up, a safety and efficacy interim analysis will be planned.

### 10.10 Interim Analysis

For the interim analysis, a DSMB will be established by the Sponsor. The DSMB will assess the safety data and the efficacy endpoints when 6-month post treatment results for the first 16 assessable patients are available. The board will also assess the available safety and efficacy data of supplementary enrolled patients.

The DSMB may decide in accordance with the Sponsor to decrease the sample size, to modify the design of the study, to continue or to stop the clinical trial.

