## ALLOB-DU1 - Clinical Study Protocol

ALLOB-DU1\_CSP | V 05 | Author: [name] | February 02, 2017 | Pg. 21/136

- **Distribution:** transportation and delivery of tissues and cells intended for human applications
- **Delayed-union (DU):** fracture that has not united within a period of time that would be considered adequate for bone healing. In this study, delayed-union is defined at the time of screening as (i) an absence of healing 3 months ( $\pm$  2 weeks) (and with a maximum of 7 months) after the onset of fracture and (ii) an absence of the progression of healing over the last 4 weeks, as confirmed by clinical and radiological evaluation.
- **Data Safety Monitoring Board (DSMB):** an independent data monitoring committee established by the Sponsor to assess at intervals the progress of a clinical trial, the safety data, and the critical efficacy endpoints, and to recommend to the Sponsor whether to continue, modify or stop the trial.
- **Eligible patient:** a screened patient who is considered eligible according to selection criteria.
- **Enrolled patient:** patient who has dated and signed the Informed Consent Form (ICF).
- **Good Clinical Practice (GCP):** set of internationally recognized ethical and scientific requirements and standards as regards the design, conduct, performance, monitoring, auditing, recording, analyses, and reporting of clinical trials, that provides assurance that the data and reported results are credible and accurate, and that the rights, safety, well-being, and confidentiality of trial subjects are protected
- **Intermediary Structure Tissue Establishment:** is an accredited tissue establishment where the activities of processing, preservation, storage or distribution of human tissues and cells are performed under an agreement with a human tissue bank (Belgian Law of December 19th 2009, the Belgian RD2 of September 28th 2009)
- **Investigating Site:** any public or private entity or medical facility where clinical trial and trial-related activities are conducted
- **Investigational Medicinal Product (IMP):** a pharmaceutical form of an active substance or Placebo being tested or used as a reference in a clinical trial.

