#### 10.5.1.2 *Type I error rate, significance tests*

In this study, two sided tests will be performed at a 5% level of significance except for efficacy analyses.

According to the Schoenfeld approach (Schoenfeld *et al.*, 1980), for the efficacy analysis, the type I error rate will be increased from the usual 5% to the 10% rate. Indeed, in this pilot single arm “proof of concept” study, it is appropriate to maintain the power and increase the type I error rate. This increases the risk of erroneously concluding that the treatment is worthy of further investigation, but does not increase the risk of missing an efficacious treatment. So in

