#### 10.5.8.3 Results of the computing

According to the 2 stages Fleming method, 20 treated patients are required (type I error rate  $\alpha$  of 5% and a statistical power of 80%). Taking into account that patients are enrolled by cohort of 4 and considering the potential heterogeneity of the population, 32 patients in total will be enrolled and treated in the study.

Step	Nb. of patients/step	Cumulated Nb. of patients	Treatment ineffective if $\Pi < 0.30$	Treatment effective if $\Pi > 0.70$
1	16 (assessable)	-	Number of successes $\leq 4$	Number of successes $\geq 12$
2	Up to 16 (assessable)	32	n.a.	n.a.

For the first 16 assessable patients, an interim analysis will be performed at the end of the 6 months follow-up (Visit #6).

The study will be prematurely stopped for:

- Safety concerns

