## ALLOB-DU1 - Clinical Study Protocol

ALLOB-DU1\_CSP

V 05

Author: [name]

February 02, 2017

Pg. 104/136

- Ineffectiveness, if less than 4 successes are observed
- Efficacy, if 12 or more successes are observed

Otherwise, additional patients will be treated in order to reach a total of 32 patients.

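### Section 10.10 lets the DSMB and sponsor cut the sample size after seeing open-label efficacy, with no criterion and no final success limit, against the instruction elsewhere to continue to 32

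*Combined protocol and SAP*

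**What the plan says.** Section 10.10 has the DSMB review safety and efficacy when the first 16 assessable patients have 6-month results, together with the efficacy data then available from later patients. It then says: "The DSMB may decide in accordance with the Sponsor to decrease the sample size, to modify the design of the study". Continuing or stopping are the other choices listed.

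The plan speaks differently elsewhere:

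- Section 10.5.8.3 stops the study for safety, for ineffectiveness or for efficacy (12 or more successes in 16), and continues: "Otherwise, additional patients will be treated in order to reach a total of 32 patients". The same section says that "32 patients in total will be enrolled and treated in the study".
- The synopsis (Interim Analysis) has recruitment continue until 32 are treated after a recommendation to continue, whether or not changes are recommended.
- The synopsis (Planned Study Period) and Section 10.7 call 32 a maximum. Section 2.5 only permits further patients. The stage-2 row of the table in 10.5.8.3 allows up to 16.
- The DSMB is defined as "an independent data monitoring committee established by the Sponsor" that recommends continuing, modifying or stopping. Section 2.5, Section 8.3.4 and the synopsis also have it recommend.

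The table in 10.5.8.3 marks both stage-2 limits as not applicable. The size calculation uses a 5% type I error, but Section 10.5.1.2 says that for efficacy "the type I error rate will be increased from the usual 5% to the 10% rate".

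**The concern.** In a two-stage design the error rates follow from the stage sizes and the limits together. Section 10.10 allows the second-stage size to be chosen once the success count is known, and the plan has no final limit. Both the size and the criterion for success are therefore open when the results are visible to the people choosing. The choice can inflate the false-positive rate or waste power, and nothing in the plan says which.

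There is also a question of governance. Elsewhere the board advises and the sponsor acts. Here the two decide together, on efficacy data, how large the study will be.

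**Working it through.** **Inputs.** p0 = 0.30 and p1 = 0.70 (10.5.8.2); alpha 5% (10.5.8.2, 10.5.8.3) or 10% (10.5.1.2); stage 1 of 16, efficacy stop at 12 or more, stage 2 up to 16 (10.5.8.3). The futility limit is 4 or fewer in the table but fewer than 4 in the text, so both are used. No final limit is stated, so every final limit below is an assumption.

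**The plan's own figure.** 10.5.8.3 says: "According to the 2 stages Fleming method, 20 treated patients are required". A two-stage Fleming design of 10 + 10 has alpha 0.0484 and power 0.977. Designs with equal stages already reach 80% power at 6 + 6 = 12 (alpha 0.0392, power 0.859). So 20 satisfies the stated targets but is not reproduced as the size they require. No overall error rate is given for 16 + 16.

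**How often the option arises.** With futility at 4 or fewer, the study continues on 5 to 11 successes. That has probability 0.550 at p = 0.30 and also at p = 0.70.

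**Formula.** Let c(n) be the smallest r with P(Bin(n, 0.30) ≥ r) ≤ alpha. With X successes in the first 16 and m further patients:

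Type I error = P(X ≥ 12) + Σ P(X = x) · P(Bin(m, 0.30) ≥ c(16 + m) − x), summed over the continuing counts x.

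**(a) Always continue to 32.** c = 15 at exact 5% gives 0.0324 (0.0327 with futility below 4), power 0.998. c = 14 at exact 10% gives 0.0677 (0.0692), power 0.999.

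**(b) A smaller total fixed in advance.** For any total from 17 to 32 with its exact 5% limit, type I error is 0.021 to 0.049. A smaller size alone does no harm to type I error.

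**(c) Total chosen after the count, to maximise the chance of success.** Nominal 5%, p = 0.30, futility at 4 or fewer:

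| x in 16 | P(X = x) | Total chosen | Limit | P(success given x) | Product |
|---|---|---|---|---|---|
| 5 | 0.2099 | 28 | 13 | 0.0095 | 0.00199 |
| 6 | 0.1649 | 28 | 13 | 0.0386 | 0.00637 |
| 7 | 0.1010 | 28 | 13 | 0.1178 | 0.01190 |
| 8 | 0.0487 | 20 | 10 | 0.3483 | 0.01695 |
| 9 | 0.0185 | 16 or 17 | 9 | 1 | 0.01854 |
| 10 | 0.0056 | 16 or 17 | 9 | 1 | 0.00556 |
| 11 | 0.0013 | 16 or 17 | 9 | 1 | 0.00130 |
| 12 or more | 0.0003 | stopped | 12 | 1 | 0.00027 |

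The sum is 0.0629 (0.0632 with futility below 4).

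At nominal 10% the same method gives 0.1245 (0.1262) if the study may end at 16. In that case 8 of 16 counts as success. If at least one patient must be added it gives 0.1078 (0.1095).

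**(d) Testing after every later patient.** This is an outer bound, relevant because 10.10 also shows the board efficacy data from later patients. With futility at 4 or fewer it is 0.087 at nominal 5%, and 0.147 to 0.158 at nominal 10%.

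**(e) Size cut but the 32-patient limit of 15 kept.**

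| Total | Type I error | Power at 0.70 |
|---|---|---|
| 20 | 0.0003 | 0.500 |
| 24 | 0.0011 | 0.850 |
| 32 | 0.0324 | 0.998 |

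**The case against.** Four points can be made for the plan.

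First, 32 is not uniformly binding. Several sections call it a maximum or make further recruitment optional, and 10.10 fits that reading. This stands: the fault is an unresolved inconsistency, not a breach of one clear rule. But none of those sections says how a smaller number would be chosen.

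Second, modifying the trial is among the recommendations the DSMB is defined to make. A reader might infer that any design change at the interim lies outside its role; the documents do not support that. What remains is narrower: a joint decision in 10.10 against a recommendation everywhere else, and a reduced size against the synopsis, which goes to 32 even with changes.

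Third, the inflated figures assume the least favourable choice at every count. At nominal 5% the excess is only about 1.3 points. The comparison with 3.3% flatters the effect, because the exact 32-patient test is conservative. The 12.6% figure requires success to be declared on 8 of 16, although the stated stage-1 limit is 12. All of this stands, so the figures are bounds.

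Fourth, this is a pilot study that deliberately tolerates more type I error (10.5.1.2), and detail is deferred to a SAP and a DSMB guidance document. Tolerance of 10% still needs a rule that delivers 10%. If the rule is meant to sit in those documents, 10.10 does not say so.

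**Conclusion.** The point holds as a conflict between sections and an unspecified adaptation. Section 10.10 allows a reduction in size without criteria, decided jointly with the sponsor after open-label efficacy is seen. It conflicts with the continue-to-32 wording in 10.5.8.3 and the synopsis, and with the recommend-only role of the DSMB.

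A reader might go further and infer that 10.10 breaks the design's nominal error rate. The documents do not support that. With no stage-2 limit and two stated alphas, there is no defined overall error rate to break. The supported statement is that type I error cannot be shown to be controlled. Its size depends on an unstated choice: up to about 6.3% at nominal 5%, or 11% to 12.6% at nominal 10%, if the exact single-stage limit is re-derived at a size chosen after the interim count; well below nominal, but with power of about 0.50 at 20 and 0.85 at 24, if an assumed limit of 15 is kept. Which futility limit is used changes little.

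**What to change.** In 10.10, delete the option to decrease the sample size. State that on efficacy the DSMB recommends either stopping or continuing to 32 under the limits in 10.5.8.3, and that any design modification it recommends goes through the amendment route in 11.9. Reconcile the two futility limits in 10.5.8.3 at the same time.

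If flexibility is wanted, pre-specify instead the permitted totals, each with its final success limit. Those limits must be computed for the whole rule, including how the total is chosen. Taking the single-stage limit for each total is what produces the 6.3%.

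In either case, deletion alone does not establish error control. Choose one efficacy alpha and fill in the final limit at 32: for example 15 or more of 32 at exact 5% (overall type I error about 3.2%) or 14 or more at exact 10% (about 6.8%). Bring the synopsis (Planned Study Period), Section 2.5, the stage-2 row in 10.5.8.3 and Section 10.7 into line on whether 32 is a target or a ceiling.

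The cost is a few sentences in an amendment, or a short table for the second option, and some loss of sponsor flexibility. Stopping for safety is unaffected.

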## ALLOB-DU1 - Clinical Study Protocol

ALLOB-DU1\_CSP

V 05

Author: [name]

February 02, 2017

Pg. 106/136

## 11 STUDY MANAGEMENT

### 11.1 Monitoring

Before study initiation, the CRA will visit the Investigating Sites to evaluate the feasibility of participating to the study (e.g., patient recruitment, staff availability, facilities, equipment). During the Study Initiation Visit, the CRA will initiate the Principal Investigator and the site staff in order to train the PI and the site staff on the Study Protocol and trial-related procedures, and verify good understanding of GCP (e.g., Investigator's responsibilities) and any other applicable Community and national legal and regulatory requirements, notably as regards standards of quality and safety for the procurement (including patient selection and inclusion), testing, distribution, administration, and traceability of human tissues and cells, as well as notification and reporting of any SAE and/or Serious Adverse Safety/Quality Events.

Very shortly after the first patient inclusion, an on-site monitoring visit will take place in order to verify the adherence to the protocol and study procedures, and thus avoiding any miscompliance in the future inclusions, if applicable.

During the course of the study, on-site monitoring visits and regular contacts with the Investigating Sites will be conducted by a monitor or the Sponsor in order to provide detailed information and support the Investigator(s), and to assess that the study is performed in compliance and accordance to the Study Protocol, ICH-GCP, and all applicable Community and national regulatory requirements.

For instance, the following aspects will be closely verified:

- Procurement of signed and dated Informed Consent
- Patient rights, including as regards protection of privacy and confidentiality of personal data and medical records, welfare, and safety
- Patient recruitment, eligibility, selection, and inclusion
- Study procedures, including laboratory and urine tests, trial-related procedures and imaging procedures
- IMP receipt, verification, and final delivery by the Pharmacist

## ALLOB-DU1 - Clinical Study Protocol

ALLOB-DU1\_CSP

V 05

Author: [name]

February 02, 2017

Pg. 107/136

- IMP receipt and verification by the Investigator
- IMP accountability and traceability
- SAE Serious Adverse Safety/Quality Events notification and reporting
- Emergency and pregnancy procedures
- Data generation and collection processes
- Accuracy of data collected and recorded in the CRF
- Facilities and Investigating Site staff
- Investigator's Trial Master File (and other on-site source documentation)

Any detected non-compliance with the Study Protocol, GCP, or any other applicable Community and national legal and regulatory requirements will be fully documented by the monitor with the explanation provided by the Investigator on a deviation log.

During the monitoring visits, the Investigator and clinical study staff should be available for questions, verification of data from the source documentation, and possible corrections to the CRF.

Following each monitoring visit, the Investigator will receive a follow-up letter detailing any actions required by either the Investigating Site staff or the monitor. Any actions must, wherever possible, be addressed immediately, or by the next scheduled monitoring visit.

The monitor will continuously be reachable and available between visits if the Investigator(s), or other study staff at the site, needs additional information and/or advice.

## 11.2 Source Documents

Each Investigating Site will maintain and archive all appropriate medical and research records related to the trial, in compliance with ICH E6 GCP Section 4.9, and regulatory and institutional requirements for the protection of patient confidentiality.

Source data are all information, original records of clinical findings, observations, or other documents in a clinical trial necessary for the reconstruction and evaluation of the trial.

## ALLOB-DU1 - Clinical Study Protocol

ALLOB-DU1\_CSP

V 05

Author: [name]

February 02, 2017

Pg. 108/136

Source documents may include, but are not limited to, a patient's medical records, hospital charts if any, clinic charts if any, the Investigator's patient study files, pharmacy dispensing records, recorded data from automated instruments, as well as the results of diagnostic tests, such as radiographs, laboratory and urine pregnancy tests.

The following information should be entered into the patient's medical record:

- Patient name, surname and date of birth
- Patient's contact information
- Medical chart (e.g. hospital source document tracking number), if any
- A statement that ICF was obtained with the date of ICF collection and a documentation on the person who conducted the Informed Consent discussion
- Dates of initial screening and all patient visits
- The patient identification number
- The study title and/or the protocol number and the name of the Sponsor
- Medical/surgical history and physical examination
- Results of blood pressure, heart rate, respiratory rate and body temperature
- Results of urine pregnancy tests (only for female with childbearing potential)
- Results of radiographs and CT Scan
- Laboratory results reports
- All concomitant medications and concurrent procedures (list of all prescription and non-prescription medications being taken at the time of entry/screening of the study. At each subsequent visit, changes to the list of medications will be recorded.)
- Occurrence and status of any AE and SAE
- The date the patient exited the study, and a notation as to whether the patient completed the study or the reason for discontinuation

**ALLOB-DU1 - Clinical Study Protocol**

ALLOB-DU1\_CSP

V 05

Author: [name]

February 02, 2017

Pg. 109/136

The questionnaires are to be completed directly by the patient (except for the Global Disease Evaluation as perceived by the physician). The original pages, considered as source data, will be kept and filed on site (in the Investigator's Trial Master File).

**11.3 Source Data Verification**

To ensure that data in the CRF are accurate and complete, and in accordance with patient source documents and other source data (e.g., laboratory results forms), 100% of source data verification (SDV) will be performed on site by the monitor such as CRA on all data and CRFs including but not limited to patient questionnaire, SAE and pregnancy-related documents, consisting in a comparison of the source documentation data with the CRFs and other records relevant to the study. This will require direct access to all original records for each patient.

Following this SDV, any errors (discrepancies) greater than 3 mm noticed on a VAS during independent verification by/on behalf of the Sponsor (e.g., audits) must trigger appropriate corrective actions to ensure exactness of all VAS values in the study.

The process of obtaining IC and the presence on file of the signed and dated ICF will be verified for all patients screened, whether or not they were considered eligible for the study.

The back-transcription of data from the CRF into source documents is not allowed, including when discrepancies/omissions are detected by SDV.

As some data will be directly entered into the CRF, the CRF will be considered as source document for these data. The "Source Data Location List" will be completed confirming the location of the source data.

**11.4 Completion of Case Report Forms, Signing, and Filing**

The patients will be monitored throughout the course of the trial and all results of evaluations will be recorded in the CRF.

CRFs will be completed for each patient screened in the trial, including screening failure patients. They will be completed as soon as possible after the patient visit. All CRFs will be checked for consistency, accuracy, and completeness, and will be dated and signed on an

**ALLOB-DU1 - Clinical Study Protocol**

ALLOB-DU1\_CSP

V 05

Author: [name]

February 02, 2017

Pg. 110/136

ongoing basis by the Investigator. This will be done as soon as possible after each patient study visit.

In addition, a personal log, detailing each site staff member working on the trial, will be kept up to date in the Investigator File. This log will record examples of each individual's handwriting, signature/initials and job title as well as the tasks the Investigator has delegated to his staff (with date of delegation). The Investigator must sign this log to indicate his/her authorisation.

The Investigator will be responsible for the punctuality, completeness, consistency and accuracy of CRFs. CRFs and related source data will be made available by the Investigator for data verification at each scheduled monitoring visit.

Completed CRF and SAE/Pregnancy-related documents will be collected by the monitor for analysis and filing. A copy of all these documents will be stored in the Investigator's archives after completion or discontinuation of the trial for a duration of 30 years according to Sponsor's SOP and European Directive.

### **11.5 Data Management**

The study Data Management Plan (DMP) will describe methods used to collect, check, and process clinical data, as well as the procedure to follow for database lock. The DMP will be developed by the CRO and/or the Sponsor and approved by the Sponsor. It will also list the roles and responsibilities of the personnel (with the corresponding functions) involved in data management process.

The database lock will be possible after approval by at least 2 authorised representatives of the Sponsor (including at least the Director of Clinical Development).

